### **8.2 Sample Size and Accrual**

The primary endpoint is disease progression free rate at the end of treatment phase 1. Disease progression is defined as either PSA progression or radiographic progression relative to baseline. The baseline value is defined as the PSA level at the beginning of treatment phase 1 (Day 29 of study). The previous Phase II studies on 5-AZA and ATRA individually demonstrated their efficacy in delaying PSA rise among prostate cancer patients. Preclinical in-vivo study demonstrated that in adjuvant setting following primary tumor surgery, animals treated with the drug combination for 4 weeks have 73% reduction on the median cell count of disseminated tumor cells in lung comparing to control animals (Personal communications between [name] and [name]).

Thus, we assume the difference in progression free rates at end of the treatment periods between drug combination and no-therapy ranges between 30% to 60% and listed various scenarios of progression-free rates in Table 1. We use McNemar test statistic to calculate the range of sample size required to differentiate the treatment from no-therapy under each scenario. The maximum sample size is required when the PSA rise is independent in the two treatment periods for the same patient. The minimum sample size is required when the PSA progression status in the two treatment periods is highly concordant. With the planned 20 patients in total, we would have >80% power to detect the difference of PSA progression rate of 20% vs 60%, with two-sided type I error of 10%. All calculation was done using PASS software.

**Table 1: Sample size using McNemar test statistic, with 80% power and 10% two-sided type I error rate.**

Sample size	P1=0.6	P2=0.7	P2=0.8
P1=0.2	14-19	8-10	10-13
P1=0.25	16-26	12-16	9-11
P1=0.3	19-35	14-20	10-13

With accrual rate of 2 patients per month, we expect to finish enrollment in 10 months. Patients who did not finish 8 weeks of drug combination treatment will be replaced but will be included for toxicity stopping rule.

### **8.3 Randomization Schema**

Since prior PSA doubling time is a known prognostic factor to disease progression, the randomization will be stratified on PSA doubling time: PSADT $\leq$ 3 months vs PSADT>3 months. A stratified block randomization of block size 1 will be used and separate randomization lists are generated in different strata (See appendix). The enrollment will continue until total number of 20 evaluable patients is reached. The target accrual number is set at 30 to account for screen failures. The maximum imbalance in each stratum is 1 and maximum total imbalance across strata is 2.

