#### STUDY SUMMARY

Title	A pilot study of the combination of 5-azacitidine (5-AZA) and all-trans retinoic acid (ATRA) for prostate cancer with PSA-only recurrence
Short Title	Prostate Cancer Dormancy
Protocol Number	
Phase	Pilot, phase 2
Methodology	Randomized, open label
Study Center(s)	Single-center
Objectives	
Primary
 

1) Evaluate disease progression-free rate at the end of Treatment Phase 1 between 5-AZA+ATRA and no-therapy.

2) Assess safety of the 5-AZA and ATRA combination therapy

 
Secondary:
 

1) Evaluate time to disease progression from start of Treatment Phase 1

2) Correlate antitumor activity and disease progression with biomarkers of dormancy in BM aspirates and peripheral blood

Number of Subjects	20 evaluable patients; the target accrual number is set at 30 to account for screen failures.

Diagnosis and Eligibility Criteria	
Diagnosis: Histologically confirmed adenocarcinoma of the prostate
 
Main inclusion criteria: 1) Rising PSA 2) PSADT <math>\leq</math> 10 months prior to initiation of ADT 2) 3) Received definitive local treatment 4) Indication for ADT 5) No evidence of regional or active distant metastases, except for regional metastases where salvage radiation therapy is not an option
 
Main exclusion criteria: 1) Patients who have received ADT and/or other chemotherapy within 3 months prior to entering the study. 2) Patients who have had radiotherapy or surgery within 4 weeks prior to entering the study. Minimally-invasive procedures for the purpose of diagnosis or staging of the disease are permitted.

Study Product(s), Dose, Route, Regimen	5-azacitidine: 40 mg/m  SQ on days 1-5 All-trans retinoic acid: 45 mg/m  PO daily (divided into 2 doses) on days 3-7 One cycle of treatment: 28 days
Duration of administration	Drugs will be administered on a 28-day cycle
Reference therapy	No reference therapy
Statistical Methodology	We will compare the disease progression-free rate at end of treatment phase 1 and time to disease progression from start of Treatment Phase 1 between 5-AZA+ATRA and no-therapy. Descriptive summary will be provided for safety endpoints and dormancy marker panel. The effect of biomarker abundance on recurrence free survival will be determined using Kaplan-Meier curves stratified across biomarker abundance groups.
Estimated enrollment period	12

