## 3. STUDY DESIGN

### **3.1 General Design**

This is a prospective, open-label, randomized, pilot study of reprogramming therapy in patients with recurrent PCa based on rising PSA only. Reprogramming therapy will include 5-azacitidine and all-trans retinoic acid. Expected duration of subject participation is 24 months.

All study will be assigned in a 1:1 randomization using computer random number generator to either the '5-AZA+ATRA' group or the 'no therapy' group. All enrollees will receive Leuprolide 7.5 mg x 1 on Day 1. On Day 29, they will initiate treatment phase 1. During this phase, patients in the '5-AZA + ATRA' group will receive treatment on a 28-day cycle, in the absence of prohibitive toxicities, for 3 cycles. During treatment phase 2, the 'no therapy' group will receive 5-AZA + ATRA on a 28-day cycle, in the absence of prohibitive toxicities, for 3 cycles. The treatment effect will be determined via comparing the intra-individual disease progression outcome at the end of the treatment phase 1, with period effect being separated through randomization. After treatment phase 1 and phase 2, all patients will be followed for a total of 24 months from the start of the study or until the events leading to discontinuation as outlined in Section 7.1 are observed. 5-AZA will be given subcutaneously on days 1-5 at a dose of 40 mg/m^2. ATRA, dosed at 45 mg/m^2 daily (divided into 2 doses), will be taken orally on days 3-7 of each cycle.

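### Section 8.3 points to an appendix for the stratum randomisation lists with no stated holder or release step, and its limit on imbalance makes half of the allocations certain to staff who know it.

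*Combined protocol and SAP*

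**What the plan says.** - **Lists.** Section 8.3 stratifies on PSA doubling time (3 months or less versus more than 3 months) and states that "separate randomization lists are generated in different strata (See appendix".
- **Blocks and balance.** The same section says "A stratified block randomization of block size 1 will be used" and "The maximum imbalance in each stratum is 1 and maximum total imbalance across strata is 2".
- **Generation.** Section 3.1 says that patients are "assigned in a 1:1 randomization using computer random number generator to either" of the two groups. It does not say when the generator is run or who sees its output.
- **Setting.** The Study Summary describes the trial as "Randomized, open label" and "Single-center".
- **Steps before treatment.** Section 4.1 requires registration before treatment starts. Section 4.2 goes from confirmed eligibility directly to leuprolide on Day 1. Neither contains a randomisation step.
- **Silence on concealment.** No section names a list holder, a central service or sealed envelopes, or fixes when the arm is revealed relative to consent and registration.
- **Other attachments.** Those identified elsewhere are a medication diary (Appendix A), budget sheets (Appendix B) and the consent form (Attachment D). The appendix with the lists has no letter.

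**The concern.** Randomisation protects a comparison only if the person deciding whether, and when, to enter a patient cannot foresee the next arm. The natural reading of Section 8.3 is that lists made in advance accompany the protocol, and nothing in the plan separates them from the people who recruit.

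Foreknowledge could be used here. Section 4.1.1 sets no threshold for a rising PSA, makes the indication for ADT a matter of judgement, accepts ECOG status up to 2 and admits some men with regional metastases. Section 4.2 lets consent and screening precede Day 1 by up to 30 days, and Section 8.2 expects 2 patients a month, so the order of entry can be shifted. Stratification balances PSADT only at the 3-month cut; other prognostic differences are left to chance.

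At stake are the first primary objective (Section 2.1, a between-arm comparison when Treatment Phase 1 ends) and time to progression (Section 2.2). With 20 evaluable patients, about 10 per arm, a few steered entries would matter.

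**Working it through.** **Inputs.** From Section 8.3: two strata, printed block size 1, maximum imbalance 1 per stratum and 2 overall. From Section 3.1: 1:1 allocation. From Section 8.2: 20 patients and a design contrast of 20% versus 60%.

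**Step 1: reproduce the plan's imbalance figures.** For an even block size *b* with 1:1 allocation, the largest running difference between arms is *b*/2 in a stratum, and twice that over two strata.

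| Block size | Per stratum | Two strata |
|---|---|---|
| 1 (as printed) | no limit; up to the stratum size | no limit |
| 2 | 1 | 2 |
| 4 | 2 | 4 |
| 6 | 3 | 6 |

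The printed block size does not give the printed limits. Block size 2 gives both.

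**Step 2: what the limit alone implies.** Stratum totals are not fixed in advance, so a limit of 1 has to hold at every count. After an even number of patients the difference is even and at most 1, so it is 0. After an odd number it is 1, and the next patient must go to the other arm. Every second allocation is therefore forced.

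**Step 3: predictability with the lists hidden.** Assume that staff know the limit, which is printed in the protocol, and the earlier allocations in the stratum, which an open-label single-centre trial makes visible.
- Certain allocations: 1 of each pair = 50%.
- Correct guesses: (0.5 + 1)/2 = 75%.
- If both strata end on an odd count among 20 patients: (20 − 2)/2 = 9 certain (45%), and (9 + 11 × 0.5)/20 = 72.5% guessed.

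**Step 4: alternatives.**

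| Situation | Certain | Guessed correctly |
|---|---|---|
| Live lists readable | 100% | 100% |
| Lists hidden, blocks of 2 | 50% | 75% |
| Lists hidden, fixed blocks of 4 | 33% | 71% |
| Lists hidden, mixed blocks of 2/4/6 (assumed sizes; simulated sequences of 20; guessing the arm that is behind) | not computed | about 70% |
| Pure chance | 0% | 50% |

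Beyond blocks of 2, readable lists add 25 points of predictability (75% to 100%).

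**Step 5: possible size of bias (assumed values).** Suppose that within strata half of the men have a better prognosis, with 60% progression-free against 20% for the rest. The false between-arm difference is the imbalance in better-prognosis share times the prognostic gap.
- 1 of 10 slots per arm steered: (0.6 − 0.4) × (0.6 − 0.2) = 0.08.
- 2 of 10 steered: (0.7 − 0.3) × (0.6 − 0.2) = 0.16.
- 2 of 10 steered, gap of only 20 points: 0.4 × 0.2 = 0.08.

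The 8 to 16 points are 20% to 40% of the 40-point design difference (0.08/0.40 and 0.16/0.40). That yardstick comes from a paired McNemar calculation, so it shows scale only.

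**Step 6: where the bias would land.** In Section 8.4 the treatment test compares each patient's period 1 minus period 2 outcome between arms, unless carryover is significant. A stable patient effect that is additive and equal in both periods cancels: 0.16 − 0.16 = 0. It does not cancel in the between-arm Chi-square test on the first period, used when carryover is significant, or in time to progression.

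**The case against.** The strongest objection is that the central fact cannot be seen. The appendix is not in the text reviewed, and it could hold the live lists, a specimen or a description of the scheme. Nor does any section say that recruiting staff hold it. This stands. A reader might infer that concealment has been lost; the documents support only that it would be lost if those two conditions hold. The absence of the appendix from this copy is not itself a fault in the plan.

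A reader might also see a conflict between Sections 3.1 and 8.3. There is none: a computer generator can produce lists in advance, and Section 3.1 does not say when it runs.

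It might further be inferred that no analysis could remove the bias. That goes too far. The planned within-patient test would offset part of it, though only part, because the outcome is binary and the patient effect need not be the same in both periods.

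Finally, the 75% figure depends on the imbalance limit being applied. If the printed block size of 1 were used literally, allocation would be simple randomisation, hidden lists would be unpredictable, and the printed limits would be wrong. Section 8.3 cannot be right on both.

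None of this supplies the missing procedure: the plan still names no list holder and no release step.

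**Conclusion.** The concern holds in conditional form. As written, the plan does not protect allocation concealment. If the appendix contains the live lists and recruiting staff have it, 100% of upcoming allocations are readable before consent. If not, the printed limit of 1 per stratum still makes 50% of allocations certain and 75% guessable to staff who know the limit and past assignments. Comparing readable lists with a 50% guess would therefore overstate what the appendix alone adds, and deleting the lists alone would not restore concealment.

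The effect on results cannot be derived from the documents. Under the stated assumptions, one or two steered slots per arm would create a false difference of 8 to 16 points in the between-arm Phase 1 comparison. Time to progression is exposed in the same way; the within-patient test is exposed less. Nothing in the documents shows that any allocation was in fact foreseen or used. The change should be made: it is specific and cheap, and it protects the first primary objective.

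**What to change.** - Keep live lists out of the protocol and its appendices; Section 8.3 should state only the method. Regenerate any slots not yet used.
- Replace the printed block size and imbalance limit with varied block sizes that are not disclosed to recruiting staff.
- Have the trial statistician, or another existing person with no part in recruitment, hold the lists.
- Release each arm one at a time, only after consent, eligibility and PSADT stratum are recorded. eRAP could do this if it supports it. Section 9.1 describes role-based access and an audit trail but no randomisation function, so this must be checked; otherwise the independent holder releases the arm.
- Add the release step to Sections 3.1 and 4.2 so that they agree with Section 8.3.

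**Cost.** Protocol wording and a set-up task, with no extra patients or visits. The maximum imbalance may exceed 1 per stratum: 2 (4 overall) if the largest block is 4, or 3 (6 overall) if it is 6. Among 20 randomised patients those worst cases are 12 versus 8 and 13 versus 7, so a largest block of 4 keeps the loss smaller.

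**What remains.** Mixed blocks of 2/4/6 lower the correct-guess rate only from 75% to about 70%. The larger gain is that a lead of one patient no longer fixes the next arm.

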### **8.4 Data analyses**

Analysis on efficacy and safety:

Patients will receive at least 8 weeks of treatment in order to be eligible for efficacy analysis. Patients who discontinued due to toxicity after 8 weeks of treatment will be included in efficacy analysis. Descriptive statistics such as mean/median/range and frequency will be provided for continuous and categorical variables separately, and the distributions of period baseline variables are contrasted between 5-AZA+ATRA and placebo using Wilcoxon statistics and Fisher's exact test statistics for continuous and categorical variables separately. Waterfall plot will be provided for PSA change relative to period baseline for all patients for each treatment arm and period. Analysis will follow the two-step procedure prescribed in for randomized crossover study for binary endpoint. To test for carryover effect, Wilcoxon rank-sum test stratified by prior PSADT will be performed to assess whether the sum of outcome variables from both periods is different between the randomization arms. If the test yields insignificant results, a similar test will be performed to compare the within-patient outcome difference between period 1 and 2 between the randomization arms to assess the treatment effect. If the carryover effect is significant, the primary analysis will be based on the progression free rates at the end of first treatment period using Chi-square test. In addition, general linear mixed model will be applied to assess the treatment effect, carryover effect, and period effect, adjusting for the stratification factor prior PSADT. The time to disease progression is defined as time to either PSA progression or radiographic progression whichever occurs first since discontinuation of ADT. Time to event endpoints will be summarized using Kaplan-Meier method. The time to event endpoints will be estimated using rank preserving failure time model (RPFTM) to obtain the counter-factual event times assuming cross-over did not occur (R package "rpfstm").

Descriptive summary will be provided for the safety endpoints. All patients who received at least one dose of study drug (treated set) will be included in the safety analysis.

Correlative analysis and biomarkers:

The micro-environmental biomarkers and dormancy biomarkers collected in this study will be described with summary statistics (mean, median, standard deviation, range) at each time point, and compared between the 5-AZA+ATRA and placebo using the Wilcoxon rank sum test statistics. Distribution of biomarkers will be examined and linear mixed model with random effects will be applied to analyze the biomarker trajectories over time. The biomarkers will be correlated with disease progression outcomes. Biomarker analysis will be performed on all patients with at least one biomarker measure at one time point (biomarker set).

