### 2.1 Primary Objectives

The co-primary objectives of the study are:

- To compare disease progression-free rate at end of Treatment Phase 1 between 5-AZA + ATRA and no-therapy.
- To assess safety of the 5-AZA and ATRA combination therapy

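### The efficacy comparison is limited to patients with at least 8 weeks of drug, with no all-randomised set, and how the rule applies to the no-therapy arm is ambiguous

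*Combined protocol and SAP*

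**What the plan says.** - **Objective (2.1).** The first co-primary objective is "To compare disease progression-free rate at end of Treatment Phase 1 between 5-AZA + ATRA and no-therapy".
- **Efficacy set (8.4).** "Patients will receive at least 8 weeks of treatment in order to be eligible for efficacy analysis". One concession follows: "Patients who discontinued due to toxicity after 8 weeks of treatment will be included in efficacy analysis".
- **Replacement (8.2, below the sample-size table).** "Patients who did not finish 8 weeks of drug combination treatment will be replaced but will be included for toxicity stopping rule". Section 8.3 adds: "The enrollment will continue until total number of 20 evaluable patients is reached".
- **Tests (8.4).** If the carryover test is not significant, "a similar test will be performed to compare the within-patient outcome difference between period 1 and 2 between the randomization arms". If it is significant, "the primary analysis will be based on the progression free rates at the end of first treatment period", using a chi-square test.
- **Power (8.2).** With 20 patients, "we would have >80% power to detect the difference of PSA progression rate of 20% vs 60" per cent, by McNemar at two-sided 10%.
- **Design (3.1).** The no-therapy arm is given the combination in Phase 2. No progression condition is attached to starting it.

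Named analysis sets exist for safety (at least one dose) and for biomarkers (at least one measurement). None contains all randomised patients for efficacy. In the efficacy text of 8.4, the reference to all patients belongs to the descriptive PSA waterfall plot.

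**The concern.** Randomisation protects a comparison only while patients stay in the groups to which they were assigned. Here a patient counts for efficacy only if he stays on drug for 8 weeks, which is known only after randomisation and may be related to outcome. Replacement restores the number of patients but not the comparability of the arms.

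The rule is also written in terms of drug, and one arm has no drug before the primary time point. Two analysts could build different datasets from the same text. With about 10 evaluable patients per arm, moving one or two patients could change the result. The plan also leaves open how a control who never starts Phase 2 is counted.

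**Working it through.** **Inputs from the documents.** McNemar test, two-sided 10%, so z = 1.645 (8.2). Rates of 60% and 20%, taken as progression-free rates as in the sample-size table; the power sentence calls them progression rates. 20 evaluable patients (8.3). Toxicity discontinuation of 4/36 = 11% in a trial of single-agent 5-AZA, at any time (5.1.5).

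**Assumptions.** Early-stopping shares f of 10, 20 and 30%; the plan gives none for this regimen before week 8. For the bias illustration: no drug effect and 40% progression-free in each phase.

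**1. The plan's own figure.** Let p10 and p01 be the two discordant probabilities, s = p10 + p01 and d = p10 − p01. Then power = Φ[(d√N − 1.645√s)/√(s − d²)].

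- Independent phases: p10 = 0.60 × 0.80 = 0.48 and p01 = 0.20 × 0.40 = 0.08, so s = 0.56 and d = 0.40. At N = 20, (1.789 − 1.231)/0.632 = 0.88, and power is 81%.
- Most concordant phases: p10 = 0.40 and p01 = 0. At N = 20, (1.789 − 1.040)/0.490 = 1.53, and power is 94%.

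Solving for 80% power gives 14 to 20 patients, against 14 to 19 in the plan. The claim reproduces for 20 evaluable patients. The planned first-line test is a stratified rank test; simulated under independent phases (two strata of 5 per arm assumed) it gave 83%, so McNemar is a fair stand-in.

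**2. The two readings of the 8-week rule.**

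| Reading | Drug-first arm | No-therapy-first arm |
|---|---|---|
| Drug in Phase 1 only | Early stoppers excluded | Nobody can be excluded |
| Each patient's own drug phase | Early stoppers excluded | Phase 1 outcome, already observed, dropped if he does not later complete 8 weeks of drug |

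Both readings condition on events after randomisation.

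**3. Bias with no drug effect.** In the worst case no early stopper is progression-free. The filtered drug-phase rate is then inflated by b = 0.40/(1 − f) − 0.40. At f = 4/36 this is 0.45 − 0.40 = 5 points. If stoppers have half the overall rate, b = (0.40 − 0.20f)/(1 − f) − 0.40 = 2.5 points.

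Let r be the within-patient correlation between phases. Filtering on one phase shifts that phase by b and the other by rb. The first-line contrast is half the difference between arms in mean (Phase 1 − Phase 2).

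- Only the drug arm filtered: b for the Phase 1 chi-square and b(1 − r)/2 for the first-line test. At 11% that is 5 points, and 2.5 points at r = 0, about 1 at r = 0.5 and 0 at r = 1.
- Each arm filtered on its own drug phase: b(1 − r) for both tests. At 11% that is 5 points at r = 0, 2.5 at r = 0.5 and 0 at r = 1.

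**4. Power with replaced patients kept in.** Recruiting to 20 evaluable patients means N = 20/(1 − f), rounded up: 22.2 gives 23, then 25, and 28.6 gives 29. The drug-phase rate is 0.60(1 − f) + 0.20f if stoppers take the control rate (56, 52, 48%), or 0.60(1 − f) if they count as failures (54, 48, 42%).

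Example at 10%, control rate, independent phases: p10 = 0.56 × 0.80 = 0.448 and p01 = 0.20 × 0.44 = 0.088, so s = 0.536 and d = 0.36. Then (1.727 − 1.204)/0.637 = 0.82, and power is 79%.

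| Assumed early stopping | N | Independent: control rate / failures | Most concordant: control rate / failures |
|---|---|---|---|
| 10% | 23 | 79% / 75% | 94% / 92% |
| 20% | 25 | 75% / 65% | 92% / 88% |
| 30% | 29 | 71% / 55% | 92% / 84% |

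**The case against.** The case for leaving the plan alone has weight. This is a pilot, and an evaluable set is common in pilots. The rule is pre-specified. Patients who stop for toxicity after 8 weeks stay in. Safety is untouched, because replaced patients remain in the toxicity rule and the treated set. Section 7.1 does not list progression among the reasons to stop drug, so the worst case, in which every stopper would have progressed, is extreme. At 11% stopping with only the drug arm filtered, the first-line bias of at most 2.5 points is small beside a design difference of 40 points.

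All of that stands and limits the severity. It does not supply an all-randomised analysis or say how the rule applies by arm, and pre-specification does not remove selection.

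Three stronger readings are tempting, and the documents do not support them:

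- *The rule is undefined for controls.* Section 8.2 speaks of 8 weeks of the combination, and 3.1 gives every patient one drug phase, so the rule can be read as each patient's own drug phase. That also suits a first-line test needing both periods. The rule is ambiguous, not undefined.
- *The power claim is wrong.* It is correct for 20 evaluable patients. Fixing N at 20 randomised patients and deducting stoppers describes a trial that the replacement rule does not produce.
- *Removed patients are lost to the endpoint.* Table 7 and 8.1 speak of removal from the trial or study, but 7.1 says that patients taken off are followed up per protocol. What is open is the schedule: in follow-up PSA is every 12 weeks, imaging is at the investigator's discretion, and follow-up ends at radiographic progression or other cancer-directed therapy (Section 7).

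**Conclusion.** The concern holds as a gap in the analysis plan that should be fixed. The randomised efficacy comparison is restricted by an event after randomisation, no all-randomised efficacy set is defined, and the rule's application to the no-therapy arm is ambiguous.

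The bias figures are illustrations. They rest on no drug effect, a 40% rate, worst-case stoppers and an 11% figure from a different regimen that counts stopping at any time.

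A reader might infer that the rule must favour the drug. Losing early stoppers in the drug phase does tend that way. But if controls who progress in Phase 1 did not go on to drug, dropping them would raise the control rate and push the other way. The plan does not say whether they go on, so the net direction is unknown.

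All-randomised power runs from 55% to 94% over the assumptions shown. It is below 80% in every independent-phase case, by about one point in the mildest, and above 80% in every most-concordant case.

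**What to change.** 1. **Efficacy set.** Make all randomised patients, analysed as randomised, the primary efficacy set, with replaced patients kept in. State one missing-outcome rule for both phases, with a sensitivity analysis, because counting missing as not progression-free can count against the drug when toxicity causes the loss. State how controls who never start Phase 2 are counted. Keep the 8-week set as a sensitivity analysis, with its rule written out by arm and phase.
2. **Data collection.** State that PSA and imaging for the primary time point continue on the treatment-phase schedule after drug stops, consistent with 7.1. Reconcile this with the follow-up limits in Section 7 and the removal wording in Table 7 and 8.1. Those two places also differ on which occurrence leads to removal; that must be reconciled separately, and no view is taken here on which is right.
3. **Power.** Say that the figure above 80% applies to 20 evaluable patients. Give the all-randomised power as a range, with its early-stopping, missing-outcome and correlation assumptions.

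The cost is protocol and SAP wording and a restated power figure, plus the treatment-phase PSA and imaging visits for patients who stop early. Replacement is already planned, so no added enrolment is asked for. The downside is a less favourable power figure at the independent-phase end and possibly a smaller estimated effect.

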## **8. STATISTICAL CONSIDERATIONS**

### **8.1 Study Design/Study Endpoints**

The primary endpoints will be the disease progression-free rate at the end of the treatment phase 1 and safety of the combination of 5-AZA and ATRA. Disease progression is defined by composite of PSA or radiographic progression relative to period baseline (start of treatment phase 1), whichever occurs first. PSA levels will be measured on day 1 of each cycle. For assessment of PSA progression, see section 3.2.1 above. CT A/P and bone scan will be performed every 3 cycles. For assessment of radiographic progression, see section 3.2.2 above. Safety will be assessed by the recording of adverse events, monitoring of vital signs and physical examinations, safety laboratory evaluations, and 12-lead ECG. Adverse events will be graded per the Common Terminology Criteria for Adverse Events (CTCAE) version 4.0. Therapy will be continued at the original dose if the adverse event is grade 0-2. For grade 3-4 toxicities, therapy will be held until improvement of symptoms to grade 2 or below. The dose will then be reduced by 25% of original for each episode. A maximum of 2 dosage reductions will be allowed. The third occurrence will result in removal of the patient from the study.

The secondary endpoints will be time to tumor progression from start of treatment phase 1 and the measurement of dormancy biomarker levels in relation to disease states: tumor progression and disease progression. To determine the relation between dormancy biomarkers and disease states, every 3 cycles, we will measure the dormancy biomarkers, TGF $\beta$ 2, BMP7, BMP4, GAS6, retinoic acid, NR2F1, in BM aspirates and peripheral blood.

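### The primary objective is a between-arm Phase 1 rate, but the default primary test and the >80% power belong to a within-patient comparison; the objective as written has about 61% power

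*Combined protocol and SAP*

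**What the plan says.** The objective in 2.1 is "To compare disease progression-free rate at end of Treatment Phase 1 between 5-AZA + ATRA and no-therapy". Section 8.1 repeats it: "The primary endpoints will be the disease progression-free rate at the end of the treatment phase 1", alongside safety. The study summary and 3.2 agree.

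Section 3.1 describes a crossover. In phase 2 the no-therapy "group will receive 5-AZA + ATRA on a 28-day cycle, in the absence of prohibitive toxicities, for 3 cycles". The same section then merges the two ideas: "The treatment effect will be determined via comparing the intra-individual disease progression outcome at the end of the treatment phase 1".

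Section 8.2 names the Phase 1 endpoint but sizes the trial with a paired McNemar calculation over two periods per patient: "The maximum sample size is required when the PSA rise is independent in the two treatment periods for the same patient". It concludes: "With the planned 20 patients in total, we would have >80% power to detect the difference of PSA progression rate of 20% vs 60" percent, at two-sided 10%. The only baseline it defines is Day 29: "The baseline value is defined as the PSA level at the beginning of treatment phase 1 (Day 29 of study").

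Section 8.4 first tests carryover with a rank-sum test on the sum of both periods' outcomes. If that is not significant, "a similar test will be performed to compare the within-patient outcome difference between period 1 and 2 between the randomization arms". If it is significant, a Phase 1 chi-square becomes primary. A mixed model with treatment, carryover and period effects is added. No significance level is stated for the pretest.

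**The concern.** Objective, primary test and power should all refer to one comparison. Here the objective is unpaired, about 10 against 10. The default test is paired within patients, and the power is for 20 pairs. A reader of the results could not tell which analysis answers the objective, and would credit that objective with a power it does not have.

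Two further things are at stake. Selecting the primary test from a pretest on the same 20 patients changes the error rate. And stable induced dormancy is the hypothesis (1.2), while no washout is stated beyond the drug-free days 8–28 of the last cycle. Benefit persisting into phase 2 is therefore plausible, and it would shrink the within-patient contrast.

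**Working it through.** **1. The plan's own figure.** Inputs from 8.2: 20 patients, two-sided 10%, rates 0.2 and 0.6, so d = 0.4. Let ψ be the discordant probability.

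- Independent periods: ψ = 0.2×0.4 + 0.6×0.8 = 0.56. Fully concordant: ψ = 0.40.
- N = [1.645√ψ + 0.842√(ψ − d²)]² / d² gives 19.4 (independent) and 13.2 (concordant). The plan prints 14–19.
- Power at 20 pairs = Φ[(d√20 − 1.645√ψ)/√(ψ − d²)]. Independent: Φ[(1.789 − 1.231)/0.632] = 81.1%. Concordant: Φ[(1.789 − 1.040)/0.490] = 93.7%.

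The stated power reproduces, as a 20-pair figure.

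**2. The comparison in the objective.** 20 evaluable patients at 1:1 (3.1, 8.2) give about 10 vs 10. Pearson X² = 20(ad − bc)²/[10·10·t(20 − t)], with t the total of one outcome, rejects at X² ≥ 1.645² = 2.706. Summing binomial probabilities over all outcomes at 20% vs 60% gives **61.4%**. The complement, 40% vs 80%, gives the same.

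- CMH over two PSADT strata (assumed splits): 61–62%.
- 11 vs 9: 63–65%. 11 vs 11: 68%. 12 vs 12: 70%.
- 80% power at 10 vs 10 needs about 20% vs 71%.

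**3. The two-stage procedure.** All paired binary outcomes for 10 + 10 patients were enumerated: a tie-corrected rank-sum on the sum (pretest), the same on the difference (default test), and Pearson chi-square on Phase 1 (fallback). Assumptions not in the documents: pretest level 10%, latent within-patient correlation 0 to 0.7, no period effect, no stratification. A share c of the drug effect persists, so the drug-first arm's phase 2 rate is 0.2 + 0.4c. Rates are taken as progression-free.

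| | c = 0 | c = 0.5 | c = 1 |
|---|---|---|---|
| Pretest not significant | 90% | 84–85% | 64–71% |
| Power, contrast without pretest | 83–97% | 60–82% | 36–53% |
| Power, two-stage as planned | 80–93% | 65–84% | 55–66% |
| Power, Phase 1 chi-square | 61% | 61% | 61% |
| Contrast's estimate of a true 40 points | 40 | 30 | 20 |

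The last row is ½{[0.6 − (0.2 + 0.4c)] − [0.2 − 0.6]} = 0.4 − 0.2c. If 20%/60% are instead progression rates, full carryover gives 44–59% without the pretest.

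Rejection under a true null, for common rates of 20% to 50%:

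- Two-stage: 12–13% with independent periods, 14–16% at correlation 0.7. Pretest levels of 5–20%, at common rates of 20% and 40%, give 11–17%.
- Contrast alone: about 10–11%.
- Phase 1 chi-square, 10 vs 10: 9–12%.

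**4. Who is evaluable.** Section 8.2 replaces patients with under eight weeks of the combination, and 8.4 requires eight weeks of treatment for efficacy. The no-therapy arm receives the combination only in phase 2. Read literally, a control's Phase 1 outcome counts only if he later completes eight weeks of phase 2 drug.

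**5. Sample-size table in 8.2.** In row P1 = 0.2 the formula in step 1 gives 10.0–13.1 for P2 = 0.7 and 7.9–9.3 for P2 = 0.8. The printed cells (8–10 and 10–13) are swapped.

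**The case against.** The strongest reply is that this is a crossover trial. Sections 3.1, 8.2 and 8.4 describe one, 8.2 also speaks of rates at the end of the treatment periods, and 8.4 models carryover and period effects. For that design the stated power is right, and the default contrast has 83% or more without carryover. This stands. A reader might infer an arithmetic error, or that the trial simply has 61% power; the documents support neither. The fault is that the objective, endpoint and fallback name a different comparison.

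Other stronger readings also fail:

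- **That the pretest gives no protection.** It gives some: with full carryover the two-stage procedure has 55–66% power, against 36–53% without it.
- **That the Phase 1 test holds exactly 10%.** The uncorrected chi-square reaches 11.6% at 10 vs 10 and 13.4% at 11 vs 11 (true rate 50%). With independent periods, the excess charged to the pretest is therefore small.
- **That any carryover hides the effect.** Only persisting benefit does. Adverse carryover (an off-drug phase 2 rate of 10% instead of 20%) raises rejection from 83% to 91%.
- **That carryover is established.** Section 1.2 reports maintenance in cell lines for at least two weeks, 1.3 calls induction by ATRA alone transient, and the dosing schedule leaves 21 drug-free days.
- **That power is only about 42%.** That is Fisher's exact test, which 8.4 plans for baseline comparisons and not for the primary endpoint.
- **That the evaluability rule favours one arm.** Section 7.1 does not list progression as a reason to stop treatment, so the size and net direction of any bias are unknown.

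The pretest level may be given in the procedure that 8.4 cites, which was not available here.

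**Conclusion.** Wrong as written. The plan's power figure is sound for 20 pairs but is not the power of its stated objective or its fallback: 61% against 81%, a gap of about 20 points. This rests on 20 evaluable patients split evenly, the plan's own rates and its two-sided 10%.

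The error inflation from the pretest is modest with independent periods and larger only under the assumed correlation and pretest level. The pretest misses most carryover, so its protection is partial. Any bias from persisting benefit is toward no effect, by an amount the documents cannot fix. The evaluability wording is a secondary point. The swapped table cells are minor: N = 20 rests on the 14–19 cell, which is unaffected.

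**What to change.** In 8.4, stop using the carryover pretest to select the test, and name one primary comparison. The choice is the sponsor's.

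**Option A, matching the objective as written.** Primary: the Phase 1 between-arm rate by CMH stratified by PSADT, with the crossover contrast and mixed model secondary. Define inclusion by one rule for both arms that uses nothing after Phase 1. In 8.2 state about 61% for 10 vs 10, or the figure for the set actually analysed (about 68% at 11 vs 11, 70% at 12 vs 12). Keep the McNemar figure only for the crossover contrast, assuming no carryover. Cost: about 20–30 points less power than the planned procedure if there is no carryover.

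**Option B, keeping the crossover contrast as primary.** Drop the pretest; reword the study summary, 2.1, 3.1, 3.2, 8.1 and 8.2 to match; state the period 2 baseline; and say that the power above 80% assumes no carryover. Cost: bias toward no effect if benefit persists, and less power than the planned procedure under full carryover (36–53% against 55–66%).

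Under either option, reconcile the sentence in 3.1, say whether 20% and 60% are progression or progression-free rates, clarify the eight-week rule for the no-therapy arm, and exchange the two table cells. These are wording changes and need no added data collection.
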